13.5.1 Efficacy Endpoints

13.5.1.1 Primary Efficacy Endpoint: Objective Response Rate

The objective response rate will be computed for all subjects with at least one measurable lesion at baseline.

13.5.1.2 Secondary Efficacy Endpoints

13.5.1.2.1 Disease Control Rate

The proportion of patients who achieve stable disease (SD) or a partial (PR) or complete (CR) response will be reported with a 95% exact binomial confidence interval.

13.5.1.2.2 Progression Free Survival

The progression-free survival estimate curves will be calculated and presented by the methods of Kaplan and Meier (1958) and 95% confidence interval will be constructed for the estimated 12-month progression-free survival rate and for the median.

13.5.1.2.3 Overall Survival

The overall survival rate will be estimated using Kaplan-Meier methodology and 95% confidence interval will be constructed for the estimated 12-month overall survival rate and for the median.

13.5.1.2.4 Time to Disease Progression

The distribution of time-to-disease progression (TTP) will be estimated using Kaplan-Meier methodology. The median and one-year estimates will be reported.

13.5.1.2.5 Duration of Disease Control

The distribution of the duration of disease control will be estimated using Kaplan-Meier methodology.

13.5.1.2.6 Degree of Neuropathy, as measured by the FACT/GOG-NTX-4 (Version 4)

The neuropathy associated with ABT-888 + 5FU and oxaliplatin will be cross tabulated with the number of cycles of therapy.

13.5.2 ORR Comparisons

13.5.2.1 ORR in patients whose tumors evidence decreased expression of or mutations in BRCA-1 or -2

ORR will be compared in patients whose tumors demonstrate evidence of decreased expression of or mutations in BRCA-1 or -2 in both pre-and post-treatment samples.

13.5.2.2 ORR in patients as a function of the PARP activity level in pre and post-treatment tumor samples

ORR will be compared in patients whose tumors exhibit low vs. high PARP activity level (as defined in section 5) in both pre-and post-treatment samples. However, for statistical purposes, only 10 patients will be evaluated for PARP activity. Thus, this efficacy endpoint will be considered as a pilot, hypothesis-generating endpoint only.

13.5.2.3 ORR in patients as a function of the expression levels of DNA repair enzymes in tumor tissues in pre and post-treatment samples

ORR will be compared in patients whose tumors exhibit low vs. high levels of the various DNA repair enzymes listed in Table 7 in both pre-and post-treatment samples. However, for statistical purposes, only 10 patients will be evaluated. Thus, this efficacy endpoint will be considered as a pilot, hypothesis-generating endpoint only.

13.5.3 Baseline Characteristics

All baseline summary statistics and analyses will be based on characteristics prior to the initiation of study drug (or randomization for non-treated subjects). Unless otherwise stated, baseline for a given variable will be defined as the last value for that variable obtained prior to the first dose of study drug.

13.5.3.1 Demographics

Age, height, weight will be summarized with means, standard error, standard deviation and range. Frequencies and percentages will be computed for the following parameter: gender, race, number of prior anti-tumor treatments, performance status, LDH status, history of previously treated brain metastases, and time since last anti-tumor treatment.

13.5.3.2 Medical Histories

Frequencies and percentages will be computed for each medical history parameter.

13.5.4 Timing of Efficacy Analyses and Safety Evaluations

As described above, this trial will follow a Simon's two-stage optimal design(1). Thus, by definition an interim efficacy analysis will be performed after the first 9 patients. A Data Safety and Monitoring Committee will also review the safety data quarterly and ensure that the early stopping rules are carried out as planned.

The date after which the 9th patient has received at least two cycles of therapy will be defined as the primary data "cutoff" date for the efficacy analyses (as detailed in Section 8). All data available at the time of database lock will be included in the efficacy and safety analyses. When data collection is complete and reviewed for completeness and all data management quality assurance (QA) and quality control (QC) procedures are

performed, the clinical database data will be extracted for documentation and statistical analyses. Once the last enrolled subject discontinues/completes the study, the study will be considered complete and all remaining data will be collected and entered into the clinical database. Overall survival will be collected on all subjects for up to 24 months after they discontinue from the study. After all survival data have been collected and entered into the clinical database, the clinical database data will be extracted once again for documentation and a "Final Analysis" will be performed on this dataset.

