One cycle will be 14 days. Patients will receive 5FU and oxaliplatin without a 5FU bolus (oxaliplatin (85mg/m²) and leucovorin (400mg/m²) on day 1, followed by a continuous infusion of 5FU (2400mg/m²) over 46 hours on days 1-3). Patients will also receive ABT-888 twice-a-day on Days 1-7 of each 14-day cycle (Figure 1).

The dose of ABT-888 will be determined by a Phase I dose escalation study. As detailed below, ABT-888 has been safely combined with traditional cytotoxic chemotherapy in previous clinical trials, though it has

not been combined with 5FU and oxaliplatin. Therefore a traditional 3+3 dose escalation approach with doses of ABT-888 ranging from 40mg to 300mg twice-a-day will be employed to determine the recommended Phase II dose of ABT-888 to be used with 5FU and oxaliplatin. Intra-patient dose escalation will not be allowed.

As of April, 2013 (updated in Version 8.0, 04-15-2013), the recommended Phase II dose has been chosen to be 200mg of ABT-888 twice a day.

Patients will be evaluated, including laboratory testing every cycle (every 14 days) and restaging studies will be performed every 4 cycles (or not more than every 12 weeks if there have been treatment delays). Patients whose tumors have not progressed at the time of restaging, as determined by RECIST 1.1 and who continue to tolerate treatment will continue on study.

The primary endpoint for Phase II will be the objective response rate (ORR), as determined by RECIST 1.1 criteria. Secondary clinical endpoints are listed above, and include the determination of the disease control rate (DCR, defined as ORR + rate of stable disease at 6 months), progression free survival (PFS), overall survival (OS), time to disease progression (TPP), duration of disease control (DDC), and tolerability and safety of the combination.

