Study activities are presented in Table 3, and an early study activities checklist through cycle 2 is detailed in Table 4. Screening will occur within 14 days, prior to administration of the first dose of ABT-888 on Day 1 (baseline imaging scans must be done within 28 days of Day 1). All patients with biopsy-able tumor deposits will undergo the pre-treatment tumor biopsy prior to cycle 1, Day 1. During cycles 1 and 2, subject assessments (physical examinations including neurologic assessment, vital signs, performance status, medication review, chemistry, hematology and adverse event evaluations) will be conducted on Day 1 of each cycle. Beginning at cycle 3, patients will be seen on Day 1 of every other cycle (i.e. C3, D1; C5, D1; C7, D1, etc). Study procedures may be performed 2 days before or after the scheduled visit date, due to unforeseen or unavoidable circumstances. The neuropathy quality of Life assessment will occur during treatment for each odd-numbered treatment. Restaging studies will be performed every 4 cycles (or not more than every 12 weeks if there have been treatment delays). Patients who are adequately tolerating therapy, and whose restaging studies reveal no evidence of disease progression, by RECIST 1.1 criteria, will continue on study for an additional 4 cycles.

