The primary endpoint of the Phase I portion is the determination of the recommended Phase II dose. The primary endpoint of the Phase II portion will be the objective response rate (ORR), as determined by RECIST 1.1 criteria. Secondary clinical endpoints are determination of the disease control rate (DCR, defined as ORR + rate of stable disease at 6 months), progression free survival (PFS), overall survival (OS), time to disease progression (TTP), duration of disease control (DDC), tolerability and safety of the combination, and degree of neuropathy, as measured by the FACT/GOG-NTX-4 (Version 4). Patients whose tumors have not progressed at the time of restaging, as determined by RECIST 1.1 criteria, and who continue to tolerate treatment will continue treatment for an additional eight weeks. When an investigator has determined that a subject should discontinue the study, a Final Visit will be conducted. Information pertaining to survival and post treatment therapy will be collected approximately every 12 weeks (Month 3, 6, 9, 12, 15 and 18) beginning after the final visit, for a period up to 24 months. Tumor biopsy procedures for the pilot subgroup are discussed in detail in section 12.

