8.2 Selection of Study Population

This is a multi-institutional study for patients with metastatic pancreatic cancer. Only patients with metastatic pancreatic cancer not amenable for resection will be considered for entry. Subjects must have measurable disease, defined as at least 1 unidimensionally measurable lesion on a CT scan as defined by RECIST.

The target recruitment for this study is 24+48 patients. At the LCCC alone, approximately 150 new cases of pancreatic cancer are seen yearly, at least one-third of which have metastatic disease. Because patients with both untreated (for metastatic disease) and pretreated cancers are eligible, most patients seen in the medical oncology clinic with metastatic disease will be eligible for this trial. As of April 2013, the enrollment criteria were modified to include only patients with a known BRCA-associate genetic mutation OR family history suggestive of a breast or ovarian cancer syndrome (as defined below), which is likely to delay enrollment. However, concurrently, the trial is opening at several centers, which may compensate for the

slower accrual. Therefore, recruitment is anticipated to take 24 – 30 months, and with each patient followed for a minimum of 8 weeks, the anticipated time to complete follow-up of all patients will be 30 – 36 months.

Subjects will undergo screening procedures within 14 days prior to administration of the first dose of ABT-888 on Day 1, unless otherwise specified (though baseline imaging scans must be done within 28 days of Day 1). Adult male and female subjects who meet all the inclusion criteria and who do not meet any of the exclusion criteria will be eligible for enrollment into the study.

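### The efficacy cutoff in 13.5.4 can fall before the 9th patient's first restaging, so the 0/9 stopping rule is not tied to nine known outcomes

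*Combined protocol and SAP*

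**What the plan says.** Section 13.5.4 plans an interim efficacy analysis after 9 patients and fixes its timing: "The date after which the 9th patient has received at least two cycles of therapy will be defined as the primary data" cutoff for the efficacy analyses, with a reference to Section 8 for detail. The same section adds "All data available at the time of database lock will be included in the efficacy and safety analyses", has data extracted "When data collection is complete and reviewed for completeness", and asks the monitoring committee to "ensure that the early stopping rules are carried out as planned".

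The assessment schedule is elsewhere:

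- Synopsis 2.5: "One cycle will be 14 days".
- Section 8.1: "Restaging studies will be performed every 4 cycles (or not more than every 12 weeks if there have been treatment delays"; patients without progression "will continue treatment for an additional eight weeks". Table 3 and Section 10.1 give the same 4-cycle interval.
- Section 8.2 plans recruitment "with each patient followed for a minimum of 8 weeks".
- Sections 10.2.4.1 and 10.2.4.2 require two observations at least 4 weeks apart for CR and PR. Section 13.4.1 defines the primary endpoint by reference to Section 10.
- Section 13.4.1 classes patients lost to follow-up without a valid assessment as non-responders. It does not mention patients whose assessment is still pending.

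Sections 2.5 and 13.2 give the rule for each stratum: stop if 0 of 9 respond; otherwise enter 15 more and accept the regimen with 3 or more responses in 24. Section 13.3 states 90% power at a 25% response rate.

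**The concern.** The cutoff is defined by treatment received, but the decision it serves depends on tumour response. The section it cites contains no two-cycle response assessment. Section 8 gives a 4-cycle restaging and an 8-week minimum follow-up, both later than two cycles.

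The 0/9 rule is the only efficacy rule that closes a stratum early, and its error rates are calculated for nine known outcomes. If the decision were taken on fewer, an active regimen would be abandoned more often than planned. The risk runs in that direction only, because the false-positive rate falls.

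**Working it through.** **Timing for the 9th patient, on schedule**

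| Event | Earliest day |
|---|---|
| Cutoff in 13.5.4: 2 × 14, counting full cycles | 28 |
| First restaging: 4 × 14 | 56 |
| Second observation if an extra scan is done: 56 + 28 | 84 |
| Second observation at the next scheduled scan: 8 × 14 | 112 |

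The gap between cutoff and first restaging is 56 − 28 = 28 days. Treatment delays can move the first scan to 12 weeks.

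**Reproducing the plan's figures.** Inputs from 2.5, 13.2 and 13.3: n1 = 9, stop at 0; n = 24, accept at 3 or more; p0 = 5%, p1 = 25%. Let X(n) be the number of responses in n patients. Then

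P(accept) = P(X(24) ≥ 3) − P(X(9) = 0) × P(X(15) ≥ 3)

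- At 25%: P(X(9) = 0) = 0.75^9 = 0.0751. Power = 0.9602 − 0.0751 × 0.7639 = 0.9028.
- At 5%: 0.95^9 = 0.6302. Alpha = 0.1159 − 0.6302 × 0.0362 = 0.0931.

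This agrees with the stated 90% power and 10% significance level.

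**One patient pending.** Suppose 0/9 is applied with 8 outcomes known and the pending patient counted as a non-responder at the interim, but with the true outcome in the final 24:

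P(accept) = P(X(24) ≥ 3) − P(X(8) = 0) × P(X(16) ≥ 3)

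- At 25%: 0.75^8 = 0.1001. Power = 0.9602 − 0.1001 × 0.8029 = 0.8798.
- At 5%: 0.95^8 = 0.6634. Alpha = 0.1159 − 0.6634 × 0.0429 = 0.0875.

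The added wrong stops at 25% are the cases where the first 8 do not respond and the 9th does: 0.75^8 × 0.25 = 0.0250, which is 0.1001 − 0.0751.

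| Outcomes known | Wrong stop at 25% | Power at 25% | Alpha at 5% |
|---|---|---|---|
| 9 | 7.5% | 90.3% | 0.093 |
| 8 | 10.0% | 88.0% | 0.087 |

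The 8-patient row needs no accrual assumption, because the 9th patient cannot have a confirmed response by day 28. Under the stated condition it is the best case. If the pending patient also stayed a non-responder in the final count, power would be 87.4%. If others of the first 9 were unconfirmed too, it would be lower: 84.9% with 7 known and 80.6% with 6. Those last two are illustrations only, since the documents give no accrual rate by stratum.

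**The case against.** The strongest reply is that the power loss needs two steps that no section contains: deciding at the earliest permitted date, and counting an unscanned patient as a non-responder. Section 13.4.1 gives that status only to patients lost to follow-up. The stopping rule requires that none of the 9 respond, which is unknown while one is unscanned. Two cycles is a minimum, data available at database lock are included, and the committee is to apply the stopping rules as planned. Section 8.2 also expects 8 weeks of follow-up.

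This stands as far as consequence goes. A reader might infer that the design has only 88% power, or that the plan stops a stratum at day 28 with unscanned patients counted as failures. The documents support neither reading, and much of the text leans towards waiting.

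It does not remove the defect. None of these passages expressly makes the 0/9 decision wait for nine outcomes. The lock is not tied to any scan. The one sentence that defines the efficacy cutoff names two cycles and cites a section that says something different.

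It is also fair that the loss is modest: 90.3 − 88.0 = 2.3 points, or 2.0 below the stated 90%.

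**Conclusion.** The cutoff sentence does not fit the endpoint or the schedule it cites, and should be corrected. That conclusion rests on the text alone.

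The effect on power is conditional. If 0/9 is applied at the earliest cutoff with the pending patient counted as a non-responder, wrong stopping at a 25% response rate is at least 10.0% instead of 7.5%, a relative increase of one third, and power is at most 88.0% instead of 90.3%. Alpha falls from 0.093 to at most 0.087, so no false-positive risk is added. If the decision waits for all nine outcomes, there is no loss. The documents neither state nor exclude the condition, so this is an inconsistent timing rule and not a demonstrated loss of power.

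The calculation takes each patient's outcome at the decision as settled. The stage-1 rule sets no time limit on response, and this point does not add one.

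**What to change.** In 13.5.4, replace the two-cycle cutoff with wording such as:

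> For each stratum, the stage-1 efficacy cutoff is the date on which all 9 stage-1 patients have a response outcome as defined in Section 10 (at least the 4-cycle restaging, plus the second observation where the first shows CR or PR) or have progressed, died or left the study without response. A stratum is stopped for 0/9 only at that date. It may proceed to stage 2 once one confirmed response is recorded.

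Correct the reference to Section 8 so that it points to the 4-cycle restaging. Stating the cutoff by stratum also settles whose 9th patient is meant, since 13.2 runs two independent designs. If a stage-1 decision has already been taken in either stratum (Section 9.4.3.3.1 shows Phase II patients already treated), record which outcomes it used.

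Sample size and decision boundaries do not change, and no scan is added. The cost is time. In a stratum without responses the stop decision comes about 4 weeks later (day 56 against day 28). If a first-scan response has to be confirmed at the next scheduled scan, it comes up to about 12 weeks later (112 − 28 = 84 days). Treatment delays would lengthen both.

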13.5.4.1 Safety Assessments

The safety of ABT-888 + 5FU and oxaliplatin will be assessed by evaluating study drug exposure, adverse events, serious adverse events, oncology-related events, all deaths, as well as changes in laboratory determinations and vital sign parameters.

13.5.4.2 Duration of Study Drug

A summarization of the number of days and/or cycles subjects were exposed to study drug will be provided.

13.5.4.3 Adverse Events

Analyses of adverse events (and Serious adverse events) will include only "treatment-emergent" events, i.e., those that have an onset on or after the day of the first dose of study drug. Analyses will not include those that have an onset greater than 30 days after the last dose of study drug. Treatment emergent adverse events will be summarized by system organ class and preferred term according to the MedDRA adverse event coding dictionary. The percentage of subjects experiencing an adverse event at a given severity, NCI CTCAE toxicity grade, and relationship to study drug will be provided.

13.5.4.4 Deaths

The number of subject deaths will be summarized (1) for deaths occurring while the subject was still receiving study drug in this study, (2) for deaths occurring off treatment within 30 days after the last dose of study drug, and (3) for all deaths in this study regardless of the number of days after the last dose of study drug.

13.5.4.5 Longitudinal Analyses of Laboratory and Vital Signs Data

Changes and/or percent changes from baseline will be analyzed for each scheduled post-baseline visit and for the final visit for blood chemistry and hematology parameters, as well as urinalysis and vital sign parameters. If more than one measurement exists for a subject on a particular day, then an arithmetic average will be calculated. This average will be considered to be that subject's measurement for that day. Post-baseline measurements more than seven days after the last dose of study drug will not be included. Subjects that do not have a baseline measurement or do not have any post-baseline measurements will not be included.

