8.3 Efficacy and Safety Assessments/Variables

8.3.1 Efficacy and Safety Measurements Assessed and Flow Chart

Study procedures for safety and exploratory efficacy assessments will be performed as summarized in Table 3, and a checklist of study activities through cycle 2 is detailed in Table 4.

Table 3: Study Activities

	Screening	Cycle 1 and Cycle 2, Day 1 ^{aaa}	Day 3 of Each Cycle	Day 1 of every odd numbered cycle (Beginning cycle 3)	Day 1 of every even numbered cycle (Beginning cycle 4)	After every 4 cycles	Off Study	Final Follow-up Visit	Every 3 months
Informed consent	X								
Demographics	X								
Medical history	X								
Concurrent meds	X	X		X			X	X	
β-HCG	X ^{bbb}	X ^{bbb}							
Dispense Medications		X		X	X				
Disconnect 5-FU			X						
Physical exam	X	X		X			X	X	
Vital signs	X	X	X	X	X		X	X	
Height	X								
Weight	X	X		X	X		X	X	
Performance Status	X	X		X			X	X	
CBC w/diff	X	X		X	X		X	X	
Serum chemistry ^{ccc}	X	X		X	X		X	X	
PT/PTT/INR	X								
Adverse event evaluation	X	X		X			X	X	
Neuropathy QOL Assessment	X			X					
PK Sampling	See Table 5 for Details								
Radiologic evaluation and Tumor Measurements	X ^{ddd}					X ^{fff}	X ^{ggg}		
Tumor Biopsy	X						X		
Research Serum Sample	X					X	X		
Progression and Survival						X		X	X

^{aaa}For the phase I portion, if any patient has been escalated from one dose cohort to another (up or down) then that particular patient will be on Day 1 of the first two cycles of the new dose level as well.

^{bbb}Urine or Serum pregnancy test (women of childbearing potential) at screening and Cycle 1, Day 1 ONLY

^{ccc}Albumin, alkaline phos, total bili, bicarbonate, BUN, calcium, chloride, creatinine, glucose, potassium, total protein, AST, ALT, sodium.

^{ddd}Screening scans should have been within 4 weeks of starting treatment.

^{eee}Optional serial samples

^{fff}But not more than every 12 weeks, if there have been treatment delays

^{ggg}If not done within the previous 4 weeks

Table 4: Early Study Activities Checklist**Screening/Pre-Treatment**

Subject Assessment	_____
Eligibility Criteria	_____
Informed Consent	_____
Pregnancy Test (if appropriate)	_____
Radiology within 4 weeks	_____
Blood for research	_____
PT/PTT/INR	_____
Tumor biopsy	_____

Cycle 1, Day 1

Subject Assessment	_____
Pregnancy Test (if appropriate)	_____
5FU, oxaliplatin, and ABT-888 Dosing	_____
ABT-888 Pharmacogenomics	_____

ABT-888 PKs (0, .5, 1, 2, 4, and 6 hours) _____

Vital Signs	_____
5-Fluorouracil disconnect	_____

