8.5.1 Discontinuation of Individual Subjects

When a subject discontinuation from the study (without reaching a protocol-defined endpoint) is planned, the investigator will notify the clinical team representative via telephone as soon as possible (provided, in each case, subject care and safety are not compromised). When a subject discontinues the study, a Final Visit will be conducted (preferably prior to the initiation of another anticancer therapy). However, these procedures should not interfere with the initiation of any new treatments or therapeutic modalities that the investigator feels are necessary to treat the subject's condition. Following discontinuation of the study drug, the subject will be treated in accordance with the investigator's best clinical judgment. At the Final Visit, the reason(s) for the discontinuation from the study will be recorded and a physical examination including neurologic assessment, body weight, vital signs measurement, laboratory analyses, performance status, tumor assessment, collection of unused study drug and an assessment of adverse events will be performed as soon as possible after discontinuation from the study. All subjects will have one Follow-Up Visit approximately 30 days after the Final Visit. This Follow-Up Visit does not need to be performed for subjects who have had a Final Visit conducted \geq 30 days after discontinuation of ABT-888. If a subject is discontinued from the study with an ongoing adverse event or an unresolved clinically significant laboratory result, the site will attempt to provide follow up until a satisfactory clinical resolution of the laboratory result or adverse event is achieved. In the event that a positive result is obtained on a pregnancy test for a subject during the study, the administration of study drug to that subject must be discontinued immediately.

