11.2 Treatments Administered

One cycle will be 14 days. Patients will receive oxaliplatin (85mg/m²) and leucovorin (400mg/m²) on day 1, followed by a continuous infusion of 5FU (2400mg/m²) over 46 hours on days 1-3. Patients will also receive ABT-888 twice-a-day on Days 1-7 of each 14-day cycle. The dose of ABT-888 in the Phase I portion will be set according to the cohort level. The dose in the Phase II portion of the study will be 200mg orally twice a day. The evening dose of ABT-888 will be taken approximately 12 hours after the morning dose, both doses with or without food. Abbott will supply ABT-888 capsules.

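### Three small defects in the descriptive safety summaries: a safety set that depends on the outcome, two CTCAE versions, and a seven-day cutoff that can remove the Final Visit from its own summary

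*Combined protocol and SAP*

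**What the plan says.** **Safety set.** Section 13.5 (Analysis Plan) includes a patient in the safety analysis on either of two grounds: having had an adverse event, or having received one cycle or more of the three study drugs. Section 13.5.4.3 then reports percentages of patients with events by severity, CTCAE grade and relationship to drug.

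**Grading scale.** Section 9.0 assesses adverse events by CTCAE 4.0. Section 9.3.3 has investigators rate severity by CTCAE 3.0. Section 9.3.8 names 4.0, but its link is to a file named for version 3.

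**Laboratory and vital-sign summaries.** Section 13.5.4.5 states: "Changes and/or percent changes from baseline will be analyzed for each scheduled post-baseline visit and for the final visit". It then limits the data: "Post-baseline measurements more than seven days after the last dose of study drug will not be included". It also says: "Subjects that do not have a baseline measurement or do not have any post-baseline measurements will not be included".

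**Timing of dosing and end visits.** Section 11.2: "Patients will also receive ABT-888 twice-a-day on Days 1-7 of each 14-day cycle". Section 8.5.1 lists laboratory tests and vital signs among the Final Visit procedures, which "will be performed as soon as possible after discontinuation from the study". It gives no limit in days. It also foresees a Final Visit 30 or more days after ABT-888 stops, because it waives the later visit in that case: "This Follow-Up Visit does not need to be performed for subjects who have had a Final Visit conducted" that late. Otherwise, "All subjects will have one Follow-Up Visit approximately 30 days after the Final Visit".

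**Where end-of-study samples are scheduled.** Sections 8.3.2.4 and 8.3.2.6 place the last vital signs and laboratory samples at the Final Visit. Table 3 in 8.3.1 marks them there (Off Study) and also under a further column, "Final Follow-up Visit".

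**The concern.** In the safety set, a patient who stops before completing a cycle counts if an event occurred and does not count otherwise. Membership is thus decided partly by the outcome being tabulated. The patients left out are all event-free, so the error can only raise the percentages.

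On grading, investigators have two conflicting instructions for the grades that 13.5.4.3 tabulates.

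On the cutoff, the same paragraph asks for a final-visit summary and applies a limit that an on-schedule end-of-cycle Final Visit misses by one day. Patients who stop after a treatment hold have later Final Visits, so the loss would be selective and could fall on patients of particular safety interest. A patient with no remaining post-baseline value leaves the summary altogether.

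**Working it through.** The plan gives no figure of its own on these points, so there is none to reproduce.

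**1. Safety set.** Let N be the patients given at least one dose, e those with the event of interest, and m those treated for less than one cycle without any adverse event. Counting all dosed patients gives e/N. The plan's rule gives e/(N − m). The ratio is N/(N − m), which is 1 or more.

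The documents do not give m. For illustration only, assume m from 0 to 3 and a true percentage of one third:

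| N | m = 0 | m = 3 | Ratio at m = 3 |
|---|---|---|---|
| 72 (24+48, section 8.1) | 24/72 = 33.3% | 24/69 = 34.8% | 72/69 = 1.043 |
| 24 (one full Phase II stratum) | 8/24 = 33.3% | 8/21 = 38.1% | 24/21 = 1.143 |

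**2. CTCAE version.** No arithmetic applies. Sections 9.0 and 9.3.3 both govern how adverse events are graded, and they name different versions. Section 9.3.8 agrees with 9.0 in its text and points to a version 3 file in its link. The documents contain neither version, so the effect on grades cannot be sized.

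**3. Seven-day cutoff.** Inputs: the last ABT-888 dose of a completed cycle is on Day 7 (11.2), and ABT-888 is the last of the three study drugs given in a cycle. The visit window is 2 days either side (8.1), and a toxicity hold may last up to 4 weeks (9.4.3.3.1). The last dose is read as the patient's final dose. Interval = visit day − 7.

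| Final Visit | Days after last dose | Result |
|---|---|---|
| Day 13 (Day 15 less 2) | 6 | kept |
| Day 14 | 7 | kept |
| Day 15 (next planned Day 1) | 8 | excluded |
| Day 17 (Day 15 plus 2) | 10 | excluded |
| After a hold of 1 to 4 weeks from Day 15 | 15 + 7 − 7 = 15 to 15 + 28 − 7 = 36 | excluded |

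*Laboratory draws affected.* On the schedule in 8.3.2.6 and 8.5.1, samples are taken on Day 1 of each cycle and at the Final Visit. Cycle 1 Day 1 is taken as pre-dose and so as baseline (13.5.3). Weekly blood counts during holds are not counted. A patient treated for k cycles then has (k − 1) + 1 = k post-baseline draws and loses 0 or 1:

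- k = 1: 0/1 to 1/1, or 0-100%
- k = 2: 0/2 to 1/2, or 0-50%
- k = 4: 0/4 to 1/4, or 0-25%

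For k = 1 with a late Final Visit, no post-baseline laboratory value remains and the patient leaves the laboratory summary.

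*Vital signs.* These are also taken on Day 3 of each cycle (8.3.2.4), so there are k + (k − 1) + 1 = 2k post-baseline readings. The loss is 0 or 1 of 2k: 0-50%, 0-25% and 0-12.5% for k = 1, 2 and 4.

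**The case against.** The best defence of the cutoff is that seven days is a deliberate on-treatment window and that the final-visit summary uses whichever Final Visit values fall inside it. That rule can be carried out. Keeping values from 30 or more days off drug, perhaps after progression or new therapy, would mix them with on-treatment values. This stands as a legitimate choice, but 13.5.4.5 does not state it, and the Final Visit is a named visit in 8.5.1. It is also fair that 8.5.1 asks for a prompt visit, that Day 13 and Day 14 visits are kept, and that no document gives the distribution of Final Visit timing. The number of patients affected is therefore unknown.

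On the safety set, 9.3.1 defines adverse events so broadly that few briefly treated patients may be event-free, and m may be near zero. That limits the size but does not make the rule sound. On grading, 13.5.4.3 need not repeat a version set elsewhere. The fault is the conflict between 9.0 and 9.3.3.

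Three stronger readings are tempting and are not supported:

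- *Every Follow-Up Visit value is collected and then always discarded.* Counting that visit, a k-cycle patient would lose 1 to 2 of k + 1 laboratory draws (50-100%, 33-67% and 20-40% for k = 1, 2 and 4). Only Table 3 schedules those samples; 8.3.2.4, 8.3.2.6 and 8.5.1 place them at the Final Visit. Because 8.3.2.6 also refers to Table 3, this is a discrepancy between table and text that needs reconciling. It does not establish a loss.
- *Undosed patients with a serious event after consent enter the denominator and pull percentages down.* Section 9.3.5 collects serious events from consent, but 9.3.1 defines an adverse event in a subject who has been given a product.
- *Late laboratory abnormalities disappear from safety review.* Section 8.5.1 requires unresolved clinically significant results to be followed, and abnormalities reported as adverse events are analysed to 30 days under 13.5.4.3.

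**Conclusion.** The point holds as a minor one, confined to descriptive safety summaries.

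The safety-set rule makes the denominator depend on the outcome. Its bias can only be upward, by a factor N/(N − m). The size is unknown and may be small; the figures for m up to 3 are illustrations, not estimates. The CTCAE conflict is plain on the text but cannot be sized.

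The cutoff can remove a Final Visit held on Day 15 or after a hold from the summary planned for it. On the schedule in the text this costs a patient at most one laboratory draw of k and one vital-sign reading of 2k. That count assumes that the final cycle's ABT-888 was taken through Day 7, that Cycle 1 Day 1 values are pre-dose, and that the Final Visit is held. Whether this is an error or an unstated on-treatment rule depends on intent, so the text needs to say which.

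The cutoff does not affect the objective response rate, the Simon decisions, DLT assessment or the 30-day adverse event window.

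**What to change.** - **13.5:** define the safety set as every patient who received at least one dose of any study drug.
- **9.0, 9.3.3 and 9.3.8:** reconcile to one CTCAE version, including the link in 9.3.8.
- **13.5.4.5:** choose one of two rules and state it. Either keep the Final Visit value of 8.5.1 in the final-visit summary whatever its timing, showing days since last dose and flagging values taken after progression or new anticancer therapy; or state that the summary is the last on-treatment value.
- **Table 3 and 8.3.2.4, 8.3.2.6 and 8.5.1:** reconcile whether laboratory tests and vital signs are taken at the Follow-Up Visit.

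The first three changes are wording only and need no new visits or samples. Under the first option for 13.5.4.5, some late values will reflect progression or later therapy, which the flag makes visible. Under the second, late Final Visit values stay out of the summary, but openly so.
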